##### **Additional exclusion criteria for xenon**

Reference:	CH
Issue:	2
Revision:	3
Issue Date:	1 May 2013
Page	33 of 49

Failure to meet any of the additional inclusion criteria for xenon listed in section 5.1.

Patients meeting the following criteria are NOT eligible for the study:

Presence of any of:

Major congenital abnormalities, imperforate anus and in particular any bowel obstruction, congenital abnormalities suggestive of chromosomal anomaly or other syndromes that include brain dysgenesis. (Neonates with congenital syndromes affecting the brain should be excluded when diagnosed).

### 5.3 Prohibited Therapies

Not Applicable.

## 6.0 Subject Assignment to Treatment Group

The babies entered into the study will be randomised into groups; xenon+cooling or cooling (standard treatment) alone. Neonates meeting all the entry criteria can be included.

Immediately after enrolment, the patient will be assigned a study ID number, chronologically, from a specified series on an enrolment log specific to the Investigational Site. The Subject's study number and date of enrolment will be entered onto the enrolment log in the Study Binder.

The babies entered into the study will be randomised into two groups on a 1:1 basis. Randomisation will be via sealed opaque envelopes containing details of treatment allocation and [an] identifying adhesive label(s) to be attached to the CRF binder. Neonates meeting all the entry criteria can be included.

## 7.0 Methods and Procedures

### 7.1 Informed Consent

Informed written consent will be obtained from a parent (only the mother can consent if parents are not married) after a full verbal and written explanation of the study by a named physician or trained nurse such as an advanced nurse practitioner. Such staff will also meet with parents during the intervention period to ensure that they understand the study procedures and continue to consent to participate in the study. Information can be given by local trained staff and consent can also be taken over the phone with the mother if she is unable to be available for the consent process (e.g. cannot be moved shortly after Caesarean Section).

Approval for the study is being obtained from the Regional South West Research Ethics Committee covering St Michael's Hospital.

Most of the patients will be born outside the study hospital (Outborn). Outborn patients are estimated to be >90% of patients. They are brought to the hospital by a dedicated retrieval team and ambulance from Bristol.

The local delivery hospitals will have medical staff (e.g. consultants, specialist registrars, advanced nurse practitioners) trained in consenting for the CoolXenon2 trial. A training log with signatures, a short CV and competency approval will be kept centrally.

Parents will receive a written information leaflet (1 page, short version) when the infant is eligible for cooling treatment. Staff will discuss CoolXenon2 with parents as soon as practically possible. Parents will be able to speak on the phone to a member of the treatment team if they need further information and help with the consent process.

Parents will also be offered the opportunity to speak to members of the treatment team that are picking up the baby for transport.

Trained staff on the transport team can take consent for the study.

A more detailed information sheet regarding the trial will be given to parents after the first conversation or at the earliest suitable time.

Which of the parents can consent to letting the child enter the trial?

- Either parent if they are married
- If the parents are not married, only the mother can consent - provided she is awake and understanding (eg not under the influence of anaesthetic drugs)

Clinical Study Protocol	Reference:	CH
Neonatal Xenon Breathing Study (CoolXenon2 Study)	Issue:	2
	Revision:	3
	Issue Date:	1 May 2013
	Page	34 of 49

- If the mother is not in a state to understand the situation and the biological father does currently not have legal parental responsibility he can assent for the trial until the mother is awake/understanding the child's condition and able to decide on consent.

A parent who is eligible to consent can, at any time and without a specific reason, withdraw the child from the study. In this situation, xenon treatment will then be stopped as soon as possible and medically safe (within minutes).

## 7.2 Pre-Study

Consent will be obtained as described above from parents of the neonates. Prior to this consent they will have been given an information leaflet describing the study and the discussion will have taken place with a Consultant Neonatologist ([name] or [name]) involved in the study or a trained member of the Transport team.

## 7.3 Screening

All infants born in St. Michael's Hospital or retrieved by ambulance from other centres to St. Michael's Hospital Neonatal ICU will have undergone a basic screen of their condition at birth as part of standard procedures, the commonest example being the APGAR scoring system, cord blood analysis and clinical examination. Any infant suspected of being in a poor condition at birth will, by locally present neonatal staff, be assessed for possible cooling as a treatment to limit brain injury using the approved entry criteria (as used in CoolCap and TOBY). Local hospitals will typically contact the St Michaels team within 1 h of age to discuss eligibility, start cooling, transport and potential inclusion in Xenon study. At this point on advice from Bristol, information on the xenon study can be given to parents.

## 7.4 Initial Assessment

The following information will be recorded on the appropriate CRFs:

### 7.4.1 Demographics

#### PATIENT

- Date of birth
- LMP last menstrual period
- EDD expected date of delivery
- Gestational age weeks, days e.g 40 weeks, 3 days
- Race
- Gender
- Weight

#### MATERNAL

- Years in education
- Labour induced on maternal indication?
- Maternal medical treatment during pregnancy

### 7.4.2 Patient History and Physical

- Delivery and resuscitation details, Review of Systems, Transport details if retrieved from another centre, Current diagnoses
- Clinical examination

### 7.4.3 Concomitant Medications

All concomitant medications will be recorded as follows:

- Medication; Start (and Stop date(s) if applicable); Indication; Dose

Clinical Study Protocol  Neonatal Xenon Breathing Study (CoolXenon2 Study)	Reference:	CH
	Issue:	2
	Revision:	3
	Issue Date:	1 May 2013
	Page	35 of 49

## 7.5 Study Phases

The study consists of:

### 7.5.1 Phase 1

Identification of potential subjects – initially using same identification method used in St. Michael's Hospital Bristol to identify infants who would benefit from cooling.

Compliance with all inclusion/exclusion criteria for use of xenon in addition to cooling (the standard treatment).

### 7.5.2 Phase 2

Formal recruitment, information supplied to / discussions with parents.  
Consent.

### 7.5.3 Phase 3

Completion of all screening / demographics / baseline data collection immediately pre-xenon, reintubation with cuffed tube, x-ray for tube placement and blood gas

Administration of 50% xenon for 18 hours to infant according to randomisation protocol.

Completion of all data collection, serum chemistry and examinations immediately post-xenon and post-cooling.

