#### **2.2 Secondary Endpoint**

A series of variables that are among the most relevant for evaluation of safety (see endpoints below) were examined closely in the previous 14 baby feasibility/safety study. We will continue to routinely monitor and record the same set of physiological variables in the proposed study, for a subset of data for a longer time period until after rewarming.

- Endpoint 1 – defined as *Mechanical ventilation and gas exchange parameters*
  - The following variables will be measured before (from start cooling), during and after xenon administration (for 12h or until 12h after end of cooling hours pending which variable):Transcutaneous oxygen saturation, end-tidal carbon dioxide concentration, blood gas data, mechanical ventilation requirements (rate, peak inspiratory pressure, inspiratory time, PEEP settings),FiO2. Average percentage xenon in inspired gas mixture (when applicable). Tracheal tube cuff pressure.
- Endpoint 2 – defined as *Haemodynamic parameters*

Reference:	CH
Issue:	2
Revision:	3
Issue Date:	1 May 2013
Page	14 of 49

- The following variables will be measured before, during and after xenon administration: Systolic, mean and diastolic arterial pressures, Heart rate.
- Endpoint 3 – defined as *Inotropic drug requirements*
  - These (drug, dose and duration) will be recorded before, during and after xenon administration until 12h after end of cooling.
- Endpoint 4 – defined as *Marker of myocardial impairment/insult*  
The following will be recorded before and after xenon administration: Plasma levels Troponin T (marker of myocardial cell death) recorded before and after xenon administration until 12h after end of cooling:
  - Endpoint 5 – defined as timecourse and peak value of *Markers of hepatic impairment*
    - These will be recorded before and after xenon administration until 12h after end of cooling: [Alanine aminotransferase , Alkaline phosphatase and Lactate Dehydrogenase]
  - Endpoint 6 – defined as timecourse and peak value of *Markers of renal impairment*
    - These will be recorded before, during and after xenon administration until 12h after end of cooling: oliguria is defined as [urine output < 1 ml/kg/h] from age > 24h, raised creatinine > 100 at > 24h of age.
  - Endpoint 7 – defined as *Evidence of infection*
    - These will be recorded: culture proven, need for antibiotics for 5 or more days, raised CRP occurring within 24h or later.

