**Cooling group**  
 Sedate, mechanically ventilate, cool.  
 If retrieved baby, cooling commenced prior to transfer to Bristol (passive or active).

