**Cooling + xenon group**  
 Sedate, mechanically ventilate for cooling.  
 Replace tracheal tube with cuffed of same or 0.5mm smaller size.  
 Inflate cuff until seal just achieved.  
 Commence cooling as in cooling-only group.  
 Commence 50% xenon in breathing gas, maintain for 18h, (cooling continuing to total of 72h).

Reference:	CH
Issue:	2
Revision:	3
Issue Date:	1 May 2013
Page	16 of 49

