## Clinical management

- 1) The neonates would be sedated, mechanically ventilated and cooled according to the protocol for cooling listed above, as this is standard treatment. In the case of retrieved babies, cooling is always started before transfer to Bristol (active or passive cooling). If not before, active cooling starts when the transport team arrives. Antibiotics, fluid management and sedative drugs used would be unmodified.
- 2) Neonates would be entered into the study according to the set criteria within a maximum of 5hrs of birth with respect to adding xenon to the existing underlying standard cooling regime which has started within 3 hrs (passive or active).

Reference:	CH
Issue:	2
Revision:	3
Issue Date:	1 May 2013
Page	18 of 49

*Specific clinical management of cooling group*

1. This group will be cooled according to the normal protocols of the hospital as this is standard treatment.

*Specific clinical management of xenon+cooling group*

After initial resuscitation and attainment of a stable state, and inclusion in the study, the tracheal tube would be replaced with a cuffed commercially available tracheal tube (Kimberley-Clark microcuff) of the same or 0.5mm smaller size as the existing one and the cuff inflated until leakage of gas around the cuff had ceased audibly and according to the ventilator monitor. This particular tube has a high volume, low pressure cuff and is specifically designed for long term use on the paediatric or neonatal intensive care unit. The cuff pressure will be monitored and recorded at the time of initial inflation, during xenon administration every 2 hours and just prior to final deflation. If there are any post extubation adverse events such as stridor, or extubation fails secondary to vocal cord, nerve or subglottic damage, these will be recorded. The experience from our recent neonatal feasibility/safety study was that of the 14 babies, one baby developed post-extubation stridor requiring steroids. \* See Appendix 4.

\*In a recent very large study of cuffed tracheal tubes for anaesthesia in infants and neonates, the use of a cuffed tube did not increase risk of post-extubation stridor. In 2246 children, post-extubation stridor was noted in 4.4% of those with a cuffed tracheal tube and 4.7% of those with uncuffed tubes, with a much lower tube exchange rate in the cuffed tube group. See Appendix 11.

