#### Assessment of causality

1. **Not related** – temporal relationship of the onset of the event, relative to the administration of the product, is not reasonable or another cause can by itself explain the occurrence of the event.
2. **Unlikely**
3. **Possibly related** – temporal relationship of the onset of the event, relative to administration of the product, is reasonable but the event could have been due to another, equally likely cause.
4. **Probably related** – temporal relationship of the onset of the event, relative to the administration of the product, is reasonable and the event is more likely explained by the product than by another cause.
5. **Definitely related** – temporal relationship of the onset of the event, relative to the administration of the product, is reasonable and there is no other cause to explain the event or a re challenge (if feasible) is positive.

Of the above definitions,

"possibly", "probably" and "definitely" related to an investigational medical product are considered adverse reactions "unlikely" and "not related" do not qualify as a causal relationship.

The severity and causality of a serious adverse event, adverse event or SUSAR (Suspected Unexpected Serious Adverse Reaction) should be assessed by a qualified medical practitioner, usually (but not always) the Chief Investigator (CI).

Adverse events or reactions that are not life threatening and do not result in death or hospitalisation may also be considered serious if they jeopardise the subject or require intervention.

All adverse events must be reported to the sponsor immediately, unless they are identified as not requiring this in the trial protocol.

It is then the responsibility of the sponsor to report the incident to the MHRA

Clinical Study Protocol  Neonatal Xenon Breathing Study (CoolXenon2 Study)	Reference:	CH
	Issue:	2
	Revision:	3
	Issue Date:	1 May 2013
	Page	41 of 49

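### Acute events at the xenon-arm-only tube exchange fall before the xenon safety window and outside the causality scale, so related-event counts can be understated

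*Protocol*

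**What the plan says.** The flow chart in section 3.0 gives the control arm as "Sedate, mechanically ventilate, cool". The xenon arm has an extra step before the gas: "Replace tracheal tube with cuffed of same or 0.5mm smaller size". Section 3.1 (Clinical management) places that step after resuscitation and stabilisation "and inclusion in the study, the tracheal tube would be replaced with a cuffed commercially available tracheal tube". Section 7.5.3 lists "baseline data collection immediately pre-xenon, reintubation with cuffed tube, x-ray for tube placement and blood gas" and only then the 18 hours of xenon.

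For ventilation and gas exchange (Endpoint 1), section 2.2 states: "The following variables will be measured before (from start cooling), during and after xenon administration". Endpoint 2 (arterial pressures and heart rate) uses the same three periods, without saying when the first one begins.

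Under Assessment of causality in section 8.5, an event is not related if the "temporal relationship of the onset of the event, relative to the administration of the product, is not reasonable" or if "another cause can by itself explain the occurrence of the event". The possible, probable and definite grades are also judged against administration of the product. Only those three count as adverse reactions. No grade refers to a study procedure.

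The tube harms that section 3.1 names for recording are late ones: "any post extubation adverse events such as stridor, or extubation fails secondary to vocal cord, nerve or subglottic damage, these will be recorded".

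**The concern.** The exchange is part of what an infant is allocated to. It follows inclusion, is done because of the study, and has no counterpart in the control arm. A desaturation, a fall in blood pressure or a failed attempt during it is a consequence of assignment to the xenon strategy. Yet the clock for both the safety windows and the causality grades starts at the gas. A harm of the strategy can then be presented as the infant's condition before treatment and graded as unconnected with the trial product.

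The Data Review Group and the planners of a larger trial of similar design need to know the safety of the whole strategy: tube exchange, breathing device and gas. In an arm of 16, one or two events filed in the wrong place could be the entire acute signal.

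**Working it through.** The plan states no figure on this point, so there is none to reproduce. The check is one of sequence and definitions, followed by a sense of scale.

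**1. Exposure.** Section 9.1 plans 16 infants per group. By the flow chart and section 3.1, the exchange applies to the xenon arm only: 16 of 16 planned, against 0 of 16.

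**2. Window.** The Endpoint 1 'before' period runs from the start of cooling to the start of xenon. The exchange comes after inclusion in an infant already being cooled (an entry criterion for xenon in section 5.1) and before xenon. It therefore lies inside 'before'. For Endpoint 2 the start of 'before' is not given, but the period ends at the same point, so a pressure drop at the exchange is again 'before'.

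**3. Causality.** Take an acute event at the exchange. Its onset precedes the product, which meets the first limb of 'not related'. The reintubation is itself a sufficient explanation, which meets the second limb. Both limbs point to the same grade, and that grade is outside the adverse reactions.

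**4. Baseline.** Read in order, section 7.5.3 puts baseline data collection first, then reintubation, x-ray and blood gas. Most baseline values may therefore precede the exchange. Only the blood gas is clearly listed after it, and the text does not say which gas is the baseline one.

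**5. Scale.** The documents give no rate of acute exchange events, so the rate *r* is an assumption. With n = 16, the expected count is 16*r* and the chance of at least one event is 1 − (1 − *r*)^16.

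| Assumed *r* | Expected events | Chance of at least one |
|---|---|---|
| 2% | 0.32 | 1 − 0.98^16 = 0.28 |
| 5% | 0.8 | 1 − 0.95^16 = 0.56 |
| 10% | 1.6 | 1 − 0.90^16 = 0.81 |
| 20% | 3.2 | 1 − 0.80^16 = 0.97 |

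These are chances that an event occurs, not that it is misclassified.

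**6. Effect of moving one event.** One related event in 16 is 6.25% (exact 95% interval 0.2% to 30.2%). If it is graded not related, the table shows 0 of 16 (0% to 20.6%). Two in 16 is 12.5% (1.6% to 38.3%). Regrading one or two events takes the related count to zero.

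**The case against.** The strongest reply is that nothing is lost.

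- Section 8.7 requires every adverse event to be recorded whatever its presumed cause.
- Section 8.8 sends all serious events to the sponsor with no filter on relatedness.
- Section 8.1 has the external group meet after any death whatever the cause, and the stopping rule in 8.3 counts deaths among xenon infants without regard to grade.
- The follow-up list in 3.2 and 7.5.4 includes air leak, hypotension needing inotropes and arrhythmia, not tied to xenon start.
- Stridor and extubation failure are named, and they arise after xenon.

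A comparison of all recorded events by arm could therefore still show an excess from the exchange. All of this stands. A reader might infer that the plan hides the harm of the xenon strategy as a whole; the documents do not support that.

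A reader might also infer that a worsened baseline biases the change from baseline in xenon's favour. That is not supported either. Section 9.1 plans descriptive statistics and a comparison of groups, and states no change-from-baseline analysis. Section 7.5.3 lists baseline collection ahead of reintubation, with only the blood gas in doubt.

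It is further fair to say that 'not related' is an inference. Grading is left to a qualified practitioner, and section 8.4 defers to a trust policy that is not shown. The inference is nonetheless direct, because both limbs of the definition are met. Section 8.8 does ask whether a test article caused the event. But the test article is the breathing device, which section 4.1 places between the ventilator and the tracheal tube, so the exchange itself remains uncovered.

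**Conclusion.** The point holds in a limited form. The safety windows and the causality scale are anchored to xenon administration rather than to randomisation or the study intervention. Acute events at an allocated, one-arm procedure therefore fall in the before-xenon period and are steered towards 'not related'. What is understated is the count of adverse reactions; what is distorted is the before/during contrast within the xenon arm. Deaths, total recorded events, serious-event reporting to the sponsor and late tube harms are not affected.

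The size cannot be fixed from the documents. Exposure is 16 against 0, and the expected number of acute events runs from 0.32 to 3.2 over assumed rates of 2% to 20%. The conclusion assumes that graders follow the scale as worded and that no separate policy adds a procedure category. This is a cheap improvement, not a defect that undermines the trial.

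**What to change.** - **Sections 2.2 and 7.5.3:** take baseline values, including the baseline blood gas, at randomisation in both arms and before any tube exchange. Keep the gas listed after reintubation as a separate, labelled value. Count safety events by arm from randomisation. The before/during/after xenon summaries can stay as a description.
- **Section 8.5:** assess causality against the study intervention (tube exchange, breathing device or xenon) by adding a grade or tick-box for relation to study procedure or device.
- **AE form:** name acute exchange events (for example desaturation, hypotension or a failed attempt) beside the late tube harms already listed.

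The cost is wording in three sections and one CRF line. The summary reports 15 infants recruited by April 2013 (8 cooling, 7 xenon); for them the same information would have to come from existing records. The downside is that the xenon arm may show slightly more related events. No clinical rule changes.

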### 7.5.4 Patient Follow-up

**Short term** information and investigations (*before discharge from hospital*):

These are part of routine clinical practice.

1. Survival
2. Duration of hospitalisation
3. Time to full oral feeds, breast or bottle
4. Hypoxic-ischaemic or other injury on MRI scan (standard sequences for this injury) preferably aged 7-12 days of age and Magnetic Resonance Spectroscopy as a part of the MRI examination if available
5. Intracranial or intraventricular haemorrhage (on MRI, CT or ultrasound)
6. Major venous thrombosis (on MRI or ultrasound)
7. Resistance Index (Doppler examination of cerebral blood flow velocities)
8. Amplitude integrated EEG (aEEG) continuously recorded until after rewarming. Assessment of time to normalisation of background activity, seizure occurrence and duration
9. Pulmonary hypertension needing treatment
10. Pulmonary haemorrhage
11. Pneumonia
12. Pulmonary air leak
13. Systemic hypotension needing inotropic support
14. Prolonged blood coagulation time assessed before xenon and at ~24 hours and/or at clinically indicated timepoints
15. Cardiac arrhythmia (not temperature induced low Heart Rate)
16. Thrombocytopenia (platelets <100,000/ul)
17. Culture proven sepsis
18. Necrotising enterocolitis, medical, radiological or surgically proven
19. Plasma markers of global (increased lactate dehydrogenase (LDH)) or cardiac compromise (increased cardiac Troponin T (cTnT))
20. Renal failure treated with dialysis

Clinical Study Protocol	Reference:	CH
Neonatal Xenon Breathing Study (CoolXenon2 Study)	Issue:	2
	Revision:	3
	Issue Date:	1 May 2013
	Page	36 of 49

Short term assessment neurological evaluation will include:

- 1) Time to recovery after birth of a normal aEEG [1]
- 2) MRI scan before 14 days of life [33, 2, 44]
- 3) Peak LDH value within 72h of life [4, 34]

We will also collect data on:

- 4) First plasma glucose after birth (usually from cord blood)
- 5) Age in hours after birth when plasma lactate has declined to <5mmol/l
- 6) Number and type of inotropic drugs needed during stay on the neonatal intensive care unit (typically the period from birth to 3-5 days of age) and the total duration in hours of any inotropic support
- 7) Number of anticonvulsant drugs given during stay on the neonatal intensive care unit.
- 8) Amount and duration of sedation (eg morphine) while ventilated mechanically on the neonatal intensive care unit.
- 9) Age at full oral feeds (breast or bottle or tube)
- 10) Outcomes of neonatal hearing screening before 14 days of life
- 11) Clinical examination at birth, at 7 days of age and at discharge including weight and head circumference

